2.4.5.3 GAIS

The GAIS aesthetic improvement (overall appearance) as determined by the subject at all applicable post-treatment time points will be a responder rate based on the subject GAIS at maximum frown at Month 1 (described in [Section 1.3.1](#)). The responder rate will be presented separately by treatment group by visit. The 95% CIs around the estimates will also be provided. The normal approximation (Wald) method will be used to calculate the 95% CIs. The actual GAIS ratings of the subject will also be presented similarly by treatment group and visit. A graph will be provided showing the responder rates over time.

CCI

CCI

2.5 Safety analysis

All safety data will be summarized descriptively based on the Safety population. All of the safety analyses will be done using OC. If deemed necessary, any analyses may be repeated using OC, BOCF, or MI as appropriate. Safety data will be included in separate data listings.

2.5.1 Extent of exposure

There will only be limited exposure to QM1114-DP since it is administered only at baseline. The number of subjects receiving a single dose of QM1114-DP and placebo, respectively, will be presented. In addition, injection characteristics will be summarized descriptively in a separate table.

2.5.2 Adverse events

All AE data will be summarized by treatment group. Missing dates will be imputed as described below. AEs will be summarized by SOC and PT. AEs occurring before treatment will be presented in listings only. The MedDRA version used for the coding will be noted as a footnote in the tables and listings. In general, percentages for the number of subjects will be calculated using the number of subjects in the safety population for the denominator.

A summary of all AEs will be provided, which will include:

- number (%) of subjects who did not have an AE
- number (%) of subjects with at least one TEAE and number of events
- number (%) of subjects and events with at least one TEAE related to study product or injection procedure and number of events
- number (%) of subjects and events with at least one TEAE not related to study product or injection procedure and number of events
- number (%) of subjects and events with at least one TEAE leading to discontinuation and number of events
- number (%) of subjects and events with at least one serious TEAE and number of events
- number (%) of subjects and events with at least one serious related TEAE and number of events
- number (%) of subjects and events with at least one AE that meets the criteria of remote spread of effect of toxin or hypersensitivity and number of events

Summaries of TEAEs (including the total number of events, number and percentage of subjects) will be displayed by treatment group according to the following:

- All TEAEs by SOC and PT
- Treatment emergent SAE by SOC, PT, maximum intensity (mild, moderate, severe), and causality
- Related TEAEs by SOC and PT, and maximum intensity (mild, moderate, severe)
- Unrelated TEAEs by SOC and PT, and maximum intensity (mild, moderate, severe)
- TEAEs leading to discontinuation by SOC and PT, and maximum intensity (mild, moderate, severe)
- TEAEs by SOC, PT, and action taken (none, medical treatment, non-pharmacological treatment, subject withdrawn)
- TEAEs that meet the criteria of remote spread of effect of toxin or hypersensitivity by SOC, PT, and maximum intensity (See [Section 2.5.2.2](#))

The number and percentage of subjects who experienced at least one of the events listed above will be summarized overall and for each SOC and each PT. System organ class and PTs will be presented in descending frequency first (by QM1114-DP group), and then alphabetically if there are ties. Each subject will contribute at most one count per summarization category. In other words, if a subject has more than one TEAE with same PT, the subject will be counted only once for that PT. Similarly, if a subject has more than one TEAE for a SOC, the subject will be counted only once in that SOC and PT. For the “action taken” summary specifically, subjects will be only counted in ‘None’ category if no other action was taken and counted in all action categories if more than one action was taken.

All related TEAEs will also be summarized by time to onset and duration. These summaries will be presented at the event level (i.e., will include multiple AEs within the same SOC and PT). Number of days to onset and duration of event will be summarized by SOC and PT, using mean, SD, minimum, maximum, and median statistics. Time to onset will be calculated as the first day with the AE *minus* the Day 0. Duration will be calculated as the last day with the AE *minus* the first day with the AE *plus* one.

[Section 2.1.3](#) lists the imputation rules for partial/completely missing dates. A completely missing stop date will not be imputed and therefore no duration will be calculated in these cases. Instead, the number of AEs that were ongoing at the end of the study will be given.

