7.2.4.2 Reporting Procedures

7.2.4.2.1 Procedures for Reporting Adverse Events

The collection of AEs is from the time that a subject signs the ICF to their final visit.

At each post-enrollment visit, the investigator (or sub-investigator) will question the subject about AEs using an open non-persuasive question to elicit reporting of AEs, for example “Have you noticed any change in your health since the last visit?” Directed questioning and examination will then be performed as appropriate.

Any AE occurring during the AE reporting period, whether it is related to the study product or not, will be recorded immediately in the source document, and described on the AE form of the eCRF along with the date of onset, severity, relationship to the study product, action taken, and outcome, without omitting any requested and known information. Additional information will be requested under certain circumstances.

At study end, AEs assessed as related to the treatment or study procedure will be monitored until they have resolved or reached a stable condition. Other AEs will be monitored until the last visit if they have not resolved or reached a stable condition.

 EST. 1981	Title 43QM2106 Clinical Study Protocol – QM1114 – GL	Doc id MA-49290
---	--	---------------------------

The investigator will maintain all pertinent medical records in the subject's study file. If necessary and approved by the subject or their legal health care representative, the investigator may contact the subject's personal physician or other health care provider(s) to obtain further details.

For SAEs (see Section [7.2.4.2.2](#)) and pregnancies (see Section [7.2.4.2.3](#)), the sponsor is to be informed immediately by e-mail. The event must be reported to the Safety e-mail within 24 hours of receipt of the information (contact details in Section [11.9](#)).

7.2.4.2.2 *Procedure for Reporting a Serious Adverse Event*

For a SAE occurring during the clinical study, regardless of whether it is related to the treatment or not, and of whether it is expected or not, the investigator must do the following:

1. Take prompt and appropriate medical action, if necessary. The safety of the subject is the first priority.
2. Ensure that the event is classified as an SAE (Section [7.2.4.1.3](#)).
3. Complete the AE form provided in the eCRF as fully as possible.

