2.1.2 Handling of Missing/Partial Dates

The handling of missing/partial dates for Adverse Events and Concomitant Medications/Procedures is outlined below. See [Section 2.4.2](#) for handling of missing data for the efficacy analyses.

While every effort will be made to obtain full, complete information on every reported medication, the following imputation rules will be followed for any respective missing medication data:

For the purpose of determining whether a medication is considered prior or concomitant, the following date imputation rules will be used. Dates will be presented as collected in the listings.

- Start Date
 - If the start date is completely missing, it will be assumed that the medication started on the study treatment date.
 - If the start date is missing the day, the first of the month will be used (i.e., UNK-JAN-2022 becomes 01-JAN-2022), provided the imputed date is on or after the subject's study treatment date; otherwise, the day of study treatment will be used.
 - If the start date is missing the month, the month of 'June' will be used (i.e., 01-UNK-2022 becomes 01-JUN-2022), provided the imputed date is on or after the subject's study treatment date; otherwise, the subsequent month after study treatment will be used.
 - If the start date is missing the year, the year of study treatment will be used (i.e., 01-JAN-UNK becomes 01-JAN-2022), provided the imputed date is on or after the subject's study treatment date; otherwise, the subsequent year after treatment will be used.
- End Date
 - If the end date is completely missing, it will be assumed that the medication is still ongoing and will not be imputed.
 - If the end date is missing the day, the last day of the month will be used (i.e., UNK-JAN-2022 becomes 31-JAN-2022).
 - If the end date is missing the month, the subsequent month after the start date will be used.
 - If the end date is missing the year, the year of study treatment will be used (i.e., 01-JAN-UNK becomes 01-JAN-2022), provided the imputed date is after the start date; otherwise, the subsequent year after start date will be used.

While every effort will be made to obtain full, complete information on every reported AE, the handling of any respective missing AE data will follow the rules above, but for adverse events. These rules will be used to calculate treatment emergence, onset time, and duration. Dates will be presented as collected in the listings.

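### AE duration borrows the medication end-date rules, which can stretch a short event with a partial stop date to weeks, and the duration statistics describe only events with a stop date

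*SAP*

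**What the plan says.** SAP 2.5.2 plans that "All related TEAEs will also be summarized by time to onset and duration", at event level by SOC and PT, "using mean, SD, minimum, maximum, and median statistics". Protocol 9.1.3.1 plans the same onset and duration summary. On the formula, the SAP states "Duration will be calculated as the last day with the AE" minus the first day, plus one.

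On absent stop dates, SAP 2.5.2 states "A completely missing stop date will not be imputed and therefore no duration will be calculated in these cases", followed by "Instead, the number of AEs that were ongoing at the end of the study will be given".

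The date rules are in SAP 2.1.2 (SAP 2.5.2 points to 2.1.3). They are introduced for deciding whether a medication is prior or concomitant, then extended to adverse events: "These rules will be used to calculate treatment emergence, onset time, and duration". For end dates, a missing day is set to the last day of the month. For a missing month, "If the end date is missing the month, the subsequent month after the start date will be used". A missing year follows a different rule, based on the treatment year, and is not at issue here. A completely missing end date is taken to mean ongoing.

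Protocol 7.2.4.2.1 says that related events at study end "will be monitored until they have resolved or reached a stable condition".

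**The concern.** A late end date does little harm when the question is only whether a medication overlapped treatment. When the same date feeds last day minus first day plus one, the imputed part becomes the result. Neither rule is bounded by the visit or contact at which the event was recorded as over, so an imputed end can fall after a visit at which the subject had already recovered.

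The second issue pulls the other way. The mean, SD, minimum, maximum and median are taken over events that have a stop date. Events that persist, or that reach a stable condition without resolving, have no duration and appear only as a count. The statistics are therefore conditional on resolution, but the SAP does not say that the table will be labelled so. Under SAP 2.1.2, an event known to have resolved but with no date would also be treated as ongoing.

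At stake is the reading of a planned safety table. With 90 active and 30 placebo subjects, many preferred terms may hold few events, so one imputed or omitted value can set the mean or the maximum.

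**Working it through.** The plan states no duration figure to reproduce. The check applies its own rules to events of known length. Inputs from the SAP are the two end-date rules (2.1.2) and duration = last day − first day + 1 (2.5.2). Event lengths, calendar and shares are assumptions.

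**Missing day, 30-day months, start day s = 1 to 30, true length 3 days**
- s = 1 to 28: the event ends in the same month, so imputed duration = 30 − s + 1, running from 30 down to 3. Sum = 462.
- s = 29 and 30: the event ends in the next month, so imputed durations are 32 and 31. Sum = 63.
- Mean = (462 + 63)/30 = 17.5 days, range 3 to 32.
- For a true 1-day event: (1 + 2 + … + 30)/30 = 15.5 days.

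On a real calendar (365 start days from 1 May 2022), the 3-day event averages 17.7 days (median 18, range 3 to 33), and 64% of start days give 14 days or more. The error is zero when the event really ended on the last day of a month.

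**Missing month**
- Start 10-JAN, stop 12-UNK becomes 12-FEB: 33 + 1 = 34 days instead of 3.
- Over the same 365 start days, a true 3-day event becomes 28 days or more for 93% of valid cases (median 34). It is exact for 6.7%, where it really crossed into the next month.
- Seven start days give a date that does not exist. Three arise from ends on 29, 30 or 31 January moved to February; four arise from ends on the 31st of March, May, August or October moved to a 30-day month. The SAP gives no fallback.

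**Effect on a table mean.** If a share f of stop dates lacks the day and every event truly lasts 3 days, the printed mean is 3(1 − f) + 17.7f.

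| f (assumed) | printed mean, days |
|---|---|
| 2% | 3.3 |
| 5% | 3.7 |
| 10% | 4.5 |
| 20% | 5.9 |

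In a small preferred term, one such date among five 3-day events gives (4 × 3 + 17.5)/5 = 5.9 days.

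**Events without a stop date.** Suppose resolved events average 5 days and a share p is unresolved after at least L days. The planned statistic stays at 5.0. A lower bound counting time to date is 5(1 − p) + pL.

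| p | L (days) | lower bound, days |
|---|---|---|
| 5% | 60 | 7.75 |
| 10% | 60 | 10.5 |
| 10% | 120 | 16.5 |
| 20% | 120 | 28.0 |

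Both p and L are assumptions, and the size of the gap depends on them.

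**The case against.** The strongest defence is that little is hidden. A reader might infer that unresolved events drop out of the safety report. They do not: SAP 2.5.2 gives the number ongoing, the related-TEAE tables by SOC, PT and intensity still include them, and listings show dates as collected. Because Protocol 7.2.4.2.1 follows related events past study end, few may lack a stop date. The SAP does not say whether post-study stop dates are used, and a stable condition supplies none.

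A reader might also infer that short events in general become weeks long, or that the mean and maximum cannot be interpreted. The documents do not support either. Only partial stop dates are affected, and not all of those. Visits on Days 1 to 4 should catch early events near onset, although the next visit is at Month 1, so later events are recalled over a longer interval. The planned median resists a few imputed values. The AE endpoints are incidence and severity; duration is a supporting description.

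These limits on scope stand. They do not repair the rules: when a partial date occurs, the imputed duration can be wrong by weeks and nothing in the table shows it. A count of ongoing events does not tell the reader that the adjacent statistics apply to resolved events only.

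**Conclusion.** The point holds for a descriptive safety table. For related TEAEs with a partial stop date, the stated rules can turn an event of 1 to 3 days into one of about 2 to 5 weeks, and the missing-month rule sometimes yields an impossible date. The per-event figures follow from the SAP's rules and an assumed calendar. The effect on a table mean depends on how many dates are partial: 3.3 to 5.9 days instead of 3 under assumed shares of 2% to 20% with the day missing.

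Separately, the duration statistics describe events with a stop date and understate duration when some events persist. No firm size can be given, because the documents report neither the share unresolved nor how long such events last. The two effects run in opposite directions and need not cancel. The primary analysis is untouched.

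**What to change.** In SAP 2.1.2, for AE duration only, replace the missing-day and missing-month end-date rules with this: use the latest valid calendar date that agrees with the recorded parts, is on or after the start date, and is not later than the visit or follow-up contact at which resolution was recorded. Study exit should not be the cap, because related events may be followed beyond it. If no such date exists, give no duration and count the event as resolved with unknown date.

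Two illustrations, with assumed visit dates:
- Start 10-JAN, stop 12-UNK, resolution recorded at a visit on 7 February: the date becomes 12-JAN, 3 days instead of 34.
- Start 3 June, stop UNK-JUN, resolution recorded on 7 June: 7 − 3 + 1 = 5 days instead of 30 − 3 + 1 = 28.

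In the SAP 2.5.2 duration table:
- label the statistics as applying to events with a stop date;
- show by PT the number with a duration, the number ongoing, and the number resolved with unknown date (Protocol 7.2.4.2.1 already collects outcome on the AE form);
- flag how many durations used an imputed date;
- correct the cross-reference from 2.1.3 to 2.1.2.

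A Kaplan-Meier summary censoring unresolved events at last contact is an optional supplement for PTs with enough events. It would need to acknowledge repeat events within a subject.

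The cost is SAP wording and minor programming, including a link from each AE to the contact that recorded resolution. Imputed durations remain upper bounds.

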2.5.2.1 Subgroup analysis

To evaluate the consistency of the AE data, subgroup analyses will be performed. All TEAEs related to study product or injection procedure by SOC, PT, and maximum intensity will be repeated by the following subgroups. The same methods specified above ([Section 2.5.2](#)) will be followed. Percentages will be calculated using the number of subjects in the safety population for each respective sub-category will be used for the denominator.

- Gender (Male, Female)
- Race (White, Black, Asian, Other)
- Fitzpatrick skin type (I-III, IV-VI)
- Site

2.5.2.2 Assessment of remote toxin spread and hypersensitivity

Any potential or suspected remote toxin spread or toxin hypersensitivity event will be evaluated separately. The identification of these events is described in [Section 1.5.1](#). Suspected remote toxin spread events and suspected toxin hypersensitivity events will be summarized in separate tables, following the same methods specified in [Section 2.5.2](#).

2.5.3 Anti-drug Antibodies (ADA)

Sampling for antibody testing will be conducted at baseline Day 0, Month 1, and Month 6. The following ADA categories will be determined based on the confirmatory assay results:

- ADA positive at any point in time, baseline or post-baseline.

- ADA positive post-baseline and positive at baseline.
- ADA positive post-baseline and not detected at baseline (treatment-induced ADA).
- ADA not detected post-baseline and positive at baseline.
- Treatment-boosted ADA, defined as a baseline positive ADA titer that was boosted to a 4-fold or higher level (greater than the analytical variance of the assay) from baseline following drug administration.
- Treatment-emergent ADA positive, defined as either treatment-induced ADA or treatment-boosted ADA.
- Persistently positive ADA, defined as having at least 2 post-baseline ADA positive measurements with at least 16 weeks (112 days) between the first and last positive measurement or an ADA positive result at the last available assessment. The category may include subject meeting these criteria who are ADA positive at baseline.
- Transiently positive ADA, defined as having at least one post-baseline ADA positive measurement and not fulfilling the conditions for persistently positive. The category may include subjects meeting these criteria who are ADA positive at baseline.
- nAb positive at any point in time, baseline or post-baseline.

The number and percentage of subjects who develop detectable ADA within each ADA response category listed above will be summarized by treatment group, including ADA prevalence and ADA incidence (proportion of ADA-positive and treatment-emergent ADA-positive subjects, respectively, in the ADA Evaluatable population). The titer values of ADA-positive subjects will be summarized descriptively (using n, min, Q1, median, Q3, max) by treatment group and visit. The kinetics of ADA development will be assessed by summarizing the number and percentage of ADA-positive subjects at each visit by treatment group.

The impact of ADA on safety data (inclusive but not limited to) any AEs, any SAEs, and any adverse events of special interest (AESIs) will be evaluated by summary statistics based on ADA status.

ADA safety tables will be summarized by treatment group and will include: (1) the number of subjects who had at least 1 AE in any category will be summarized by ADA category (ADA positive, ADA negative, treatment-emergent ADA positive, and nAb positive); (2) a summary of subjects with injection site reactions or hypersensitivity events by ADA status will be presented; (3) a data listing of adverse events among subjects who developed anti-drug antibodies.

A line plot of ADA positivity in each treatment group will be presented by visit. A box plot of titer values in each treatment group will be presented by visit.

If there are more than 20 subjects in the QM1114-DP treatment group who are treatment-emergent ADA positive, a summary of the duration and onset of ADA may be generated as well as the impact of ADA on the primary efficacy endpoint.

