2.1.4 Safety Objectives and Endpoints

The safety objective is to evaluate the safety of a single dose of 50U of QM1114-DP and placebo in the treatment of moderate to severe GL.

Endpoints:

- Incidence and severity of treatment emergent AEs (TEAEs)
- FPE findings
- Vital signs
- Neutralizing antibody production

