5.2.1 Inclusion Criteria

1. Male or female, 18 years of age or older.
2. **CCI**
[REDACTED]
3. [REDACTED]
4. Previous repeated treatments with BoNT-A products for aesthetic use within 3 years prior to the screening visit.
5. Female of non-childbearing potential (i.e., post-menopausal [absence of menstrual bleeding for 1 year prior to screening, without any other medical reason], or has undergone hysterectomy or bilateral oophorectomy).

OR

Female of childbearing potential with a negative urine pregnancy test at screening and baseline, and agrees to use a highly effective and approved contraceptive method for the duration of the study. A highly effective method of contraception is defined as:

- Bilateral tubal ligation;
- Combined (estrogen and progesterone containing) oral, intravaginal or transdermal contraceptives that inhibit ovulation as the primary mode of action, on a stable dose for at least 28 days prior to screening visit;
- Intrauterine device (IUD) inserted at least 28 days prior to screening visit;
- Intrauterine hormone-releasing system;
- Partner vasectomized for at least three months prior to screening visit;

CONFIDENTIAL

Page 32 of 86

	
Title 43QM2106 Clinical Study Protocol – QM1114 – GL
	
Doc id MA-49290

--	--	-----------------------------------

Effective date: 2022-03-21 13:08

Effective

Version: 3.0

- Progestogen-only oral, injectable or implantable contraceptives that inhibit ovulation as the primary mode of action, on a stable dose for at least 28 days prior to screening visit; or
- Strict abstinence (i.e., refraining from heterosexual intercourse for the duration of the subject's participation in the study).

6. Time and ability to complete the study and comply with instructions.
7. Understands the study requirements and signed the informed consent form (ICF).

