1.5.4 Anti-drug Antibodies (ADA)

Blood samples will be taken for measurement of serum neutralizing antibody testing against QM1114-DP at baseline (before treatment), Month 1, and Month 6.

Analysis of the blood samples include in vitro screening and confirmatory (if positive screening result) ELISA assays to test for the presence of binding antibodies, and in vivo mouse protection assay (MPA) to test for the presence of neutralizing antibodies. The MPA will only be conducted if the subject has a positive confirmatory result. ADA categories outlined in [Section 2.5.3](#) will be determined based on the confirmatory assay results.

2 Statistical Methods

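### SAP 2.5.3 summarizes neutralizing antibody (nAb) only as any-time positivity, so the protocol's endpoint of nAb production has no planned estimate

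*SAP*

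**What the plan says.** Protocol 2.1.4 lists "Neutralizing antibody production" among the safety endpoints, and the synopsis specifies antibodies against QM1114-DP. Protocol 7.2.3 takes blood before treatment, at Month 1 and at Month 6. Inclusion criterion 4 (Protocol 5.2.1) requires "Previous repeated treatments with BoNT-A products for aesthetic use within 3 years prior to the screening visit".

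SAP 1.5.4 sets out tiered testing: a screening ELISA, a confirmatory ELISA for binding antibody, then a mouse protection assay (MPA) for neutralizing antibody. On the last step it says "The MPA will only be conducted if the subject has a positive confirmatory result".

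SAP 2.5.3 then lists the response categories. For ADA it separates baseline from post-baseline status and defines treatment-induced and treatment-boosted antibody, leading to "Treatment-emergent ADA positive, defined as either treatment-induced ADA or treatment-boosted ADA". It also defines persistent and transient ADA. For nAb it has one entry: "nAb positive at any point in time, baseline or post-baseline". The by-visit summary is for ADA as well: "The kinetics of ADA development will be assessed by summarizing the number and percentage of ADA-positive subjects at each visit by treatment group". The adverse-event table by antibody status, later in the same section, has an nAb-positive group that is not divided by time of onset.

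**The concern.** Production means antibody that was not there before treatment, and the pre-treatment sample is what allows that to be judged. The single nAb category discards the distinction. The SAP makes it carefully for ADA but not for the antibody type that the protocol names as its endpoint, and it gives no reason.

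The population makes this relevant. Every subject has had repeated BoNT-A, so some may carry nAb at baseline. A nonzero any-time rate would then leave the reader unable to tell old antibody from new in the tables, and adverse events in the nAb-positive group could not be related to nAb arising after treatment.

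**Working it through.** The plan states no nAb figure, so there is nothing to reproduce. The check has two parts.

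**1. What the planned rows identify.**

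- The any-time nAb row merges baseline-only, post-baseline-only and both-times positives. No nAb shift table, nAb-by-visit summary or treatment-emergent nAb row is specified elsewhere in the SAP.
- Treatment-emergent ADA is not a proxy. It includes binding antibody that does not neutralize. It also misses a subject who is ADA positive and MPA negative at baseline, has no 4-fold titer rise, and turns MPA positive after treatment.
- The two rows for ADA positive after baseline (one with ADA at baseline, one without) do give something. If the MPA is run sample by sample, a subject who is nAb positive after treatment must be ADA positive after baseline. The sum of the two rows is then an upper bound on new nAb. It is a bound, not an estimate.

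**2. How far the any-time rate can stand from production.** Inputs: 90 active and 30 placebo subjects (Protocol 5.1). Baseline nAb prevalence *b* and incidence *i* among baseline-negative subjects are not in the documents; the values below are assumptions.

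Any-time rate = *b* + (1 − *b*)·*i*. Expected new cases among 90 = 90·(1 − *b*)·*i*. Pre-existing share = *b* / any-time rate.

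| *b* | *i* | Any-time rate | Expected positives of 90 | Expected new cases | Pre-existing share |
|---|---|---|---|---|---|
| 0% | 5% | 5.0% | 4.5 | 4.5 | 0% |
| 5% | 0% | 5.0% | 4.5 | 0 | 100% |
| 5% | 1% | 5.95% | 5.36 | 0.86 | 84% |
| 1% | 1% | 1.99% | 1.79 | 0.89 | 50% |

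The first two rows show the same 5.0% with opposite meanings. A treatment-emergent row among baseline-negative subjects would show 5%, 0%, 1% and 1% in turn.

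In whole subjects: with 1, 2 or 3 baseline-only positives among 90 and no new nAb, the planned row reads 1/90 = 1.1%, 2/90 = 2.2% or 3/90 = 3.3%, with Clopper-Pearson 95% upper limits of 6.0%, 7.8% and 9.4%. Production would be 0/90, with upper limit 1 − 0.025^(1/90) = 4.0%. In placebo, one such subject adds 1/30 = 3.3 points.

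Placebo offers only an indirect correction. The approximate 95% half-width for the difference in any-time rates is 1.96·√[p(1 − p)(1/90 + 1/30)]. For common rates p of 2%, 5% and 10% this is 5.8, 9.0 and 12.4 percentage points, and the SAP plans only descriptive summaries here.

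**The case against.** The strongest case on the other side is that this is a descriptive safety summary with no hypothesis attached, and that the information is not lost. SAP 2.1 and 2.5 promise listings, so with a handful of positives each case could be classified by hand. The tiered assay makes the post-baseline ADA rows an upper bound, and if both are zero, so is nAb production. All of this stands, subject to the per-sample reading of the MPA rule. It limits the seriousness, but it does not supply a prespecified estimate of a protocol endpoint; a count assembled from listings after unblinding would be post hoc.

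A reader might go further than the documents allow in four ways:

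- **That the plan attributes pre-existing nAb to QM1114-DP.** It does not. The row is openly labelled as including baseline and is shown by randomized arm, with placebo subjects recruited under the same prior-toxin criterion.
- **That the trial cannot report its endpoint.** The samples and assays needed are planned. Only the summary is missing.
- **That nAb would be derived from the wrong assay.** SAP 1.5.4 says the ADA categories "will be determined based on the confirmatory assay results", and the nAb row sits in a list with the same lead-in in 2.5.3. But 1.5.4 also assigns neutralizing antibody to the MPA, so this is loose wording only.
- **That the distortion is known to be material.** No baseline prevalence is given, and the assay targets antibody against QM1114-DP, so how far earlier products would produce a positive result is not quantified.

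The adverse-event table does not restate the any-time definition for its nAb-positive group. That the definition carries over is likely, but it is an inference.

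**Conclusion.** The point holds as a gap in the planned summaries. SAP 2.5.3 measures nAb prevalence where the protocol endpoint is nAb production, and no other planned row estimates production; the post-baseline ADA rows at most bound it from above. The size is unknown. It depends wholly on baseline nAb prevalence: zero if no subject is nAb positive at baseline, and 1.1 to 3.3 points in the active arm if 1 to 3 of 90 are positive at baseline only. Those counts are assumptions, and 90 is the planned arm size rather than the number with evaluable samples. The primary efficacy analysis is not affected. The change is worth making before database lock because it is cheap and concerns a named endpoint.

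**What to change.** In SAP 2.5.3:

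1. Add treatment-emergent nAb: not nAb positive at baseline (MPA negative, or ADA negative so that the MPA was not run) and MPA positive at Month 1 or Month 6.
2. Summarize it by treatment group and visit, among subjects with a baseline result and at least one later result. State this denominator explicitly, since the ADA-evaluable population named in 2.5.3 is not defined in SAP 2.2.
3. Report baseline nAb positivity as its own row, and keep the any-time row labelled as prevalence.
4. Add the treatment-emergent nAb category to the adverse-event table by antibody status.
5. State that nAb status comes from the MPA.

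The cost is SAP wording and a few table rows, using samples and assays already planned. No visit, sample size or significance level changes.
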